### 4.2 Secondary Endpoints and Assessment Methods

See Section 9.2 of the protocol.

### 4.3 Observational Endpoints and Assessment Methods

There are no observational objectives in this study.

### 4.4 Derived Endpoints: Calculation Methods

#### 4.4.1 Safety

The solicited period for solicited injection site reactions is from Day (D) 0 to D7 and from D0 to D14 for solicited systemic reactions.

Table 4.1, Table 4.2, and Table 4.3 present, respectively, the injection site reactions and systemic reactions that are prelisted in the DCs and case report form (CRF) for the different age group, together with the intensity scales.

**Table 4.1: Solicited injection site reactions: terminology, definitions, and intensity scales for subjects aged 9 to 11 years**

CRF term (MedDRA lowest level term [LLT])	Injection site pain	Injection site erythema	Injection site swelling
DC term	Pain	Redness	Swelling
Definition		Presence of a redness including the approximate point of needle entry	Swelling at or near the injection site Swelling or edema is caused by a fluid infiltration in tissue or cavity and, depending on the space available for the fluid to disperse, swelling may be either soft (typically) or firm (less typical) to touch and thus can be best described by looking at the size of the swelling
Intensity scale*	Grade 1: Easily tolerated  Grade 2: Sufficiently discomforting to interfere with normal behavior or activities  Grade 3: Incapacitating, unable to perform usual activities	Grade 1: > 0 to < 25 mm  Grade 2: ≥ 25 to < 50 mm  Grade 3: ≥ 50 mm	Grade 1: > 0 to < 25 mm  Grade 2: ≥ 25 to < 50 mm  Grade 3: ≥ 50 mm

\* For the subjective reaction of pain, subjects or parents/legally acceptable representatives recorded the intensity level (Grade 1, 2, or 3) in the DC. For the measurable reactions of redness and swelling, they recorded the size of the reaction and the classification as Grade 1, 2, or 3 will be assigned at the time of the statistical analysis.

**Table 4.2: Solicited injection site reactions: terminology, definitions, and intensity scales for subjects aged  $\geq 12$  years for all subjects**

CRF term (MedDRA LLT)	Injection site pain	Injection site erythema	Injection site swelling
DC term	Pain	Redness	Swelling
Definition		Presence of a redness including the approximate point of needle entry	Swelling at or near the injection site Swelling or edema is caused by a fluid infiltration in tissue or cavity and, depending on the space available for the fluid to disperse, swelling may be either soft (typically) or firm (less typical) to touch and thus can be best described by looking at the size of the swelling
Intensity scale*	Grade 1: No interference with activity Grade 2: Some interference with activity Grade 3: Significant; prevents daily activity	Grade 1: $\geq 25$ to $\leq 50$ mm Grade 2: $\geq 51$ to $\leq 100$ mm Grade 3: $> 100$ mm	Grade 1: $\geq 25$ to $\leq 50$ mm Grade 2: $\geq 51$ to $\leq 100$ mm Grade 3: $> 100$ mm

\* For the subjective reaction of pain, subjects/parents/legally acceptable representatives recorded the intensity level (Grade 1, 2, or 3) in the DC. For the measurable reactions of redness and swelling, they recorded the size of the reaction and the classification as Grade 1, 2, or 3 will be at the time of the statistical analysis

**Table 4.3: Solicited systemic reactions: terminology, definitions, and intensity scales**

CRF term (MedDRA LLT)	Fever	Headache	Malaise	Myalgia	Asthenia
DC term	Temperature	Headache	Feeling unwell	Muscle aches and pains	Weakness
Definition	Elevation of temperature to $\geq 38.0^{\circ}\text{C}$ ( $\geq 100.4^{\circ}\text{F}$ )	Pain or discomfort in the head or scalp. Does not include migraine.	General ill feeling. Malaise is a generalized feeling of discomfort, illness, or lack of well-being that can be associated with a disease state. It can be accompanied by a sensation of exhaustion or inadequate energy to accomplish usual activities.	Muscle aches and pains are common and can involve more than one muscle at the same time. Muscle pain can also involve the soft tissues that surround muscles. These structures, which are often referred to as connective tissues, include ligaments, tendons, and fascia (thick bands of tendons). Does not apply to muscle pain at the injection site which should be reported as injection site pain.	Generalized weakness.
Intensity scale*	Grade 1: $\geq 38.0^{\circ}\text{C}$ to $\leq 38.4^{\circ}\text{C}$ , or $\geq 100.4^{\circ}\text{F}$ to $\leq 101.1^{\circ}\text{F}$  Grade 2: $\geq 38.5^{\circ}\text{C}$ to $\leq 38.9^{\circ}\text{C}$ , or $\geq 101.2^{\circ}\text{F}$ to $\leq 102.0^{\circ}\text{F}$  Grade 3: $\geq 39.0^{\circ}\text{C}$ or $\geq 102.1^{\circ}\text{F}$	Grade 1: No interference with activity  Grade 2: Some interference with activity  Grade 3: Significant; prevents daily activity	Grade 1: No interference with activity  Grade 2: Some interference with activity  Grade 3: Significant; prevents daily activity	Grade 1: No interference with activity  Grade 2: Some interference with activity  Grade 3: Significant; prevents daily activity	Grade 1: No interference with activity  Grade 2: Some interference with activity  Grade 3: Significant; prevents daily activity

\* For all reactions but fever, subjects or parents/legally acceptable representatives recorded the intensity level (Grade 1, 2, or 3) in the DC. For fever, they recorded the body temperature and the classification as Grade 1, 2, or 3 will be assigned at the time of the statistical analysis.

#### 4.4.1.1 **Solicited Reactions**

##### 4.4.1.1.1 **Daily Intensity**

Intensity will be categorized as follows: None, Grade 1, Grade 2, Grade 3, or Missing. The daily intensity will be recorded by the Investigator for solicited reactions whose scale is not a measure. For measurable solicited reactions, the intensity will be calculated at the time of the statistical analysis based upon the intensity scales defined in the protocol.

A reaction that is too large to measure (non-measurable [NM]) will be considered as Grade 3.

##### 4.4.1.1.2 **Maximum Overall Intensity**

Maximum overall intensity is derived from the daily intensities and is calculated as the maximum of the daily intensities over the period considered. The maximum intensity during the solicited period will be computed without considering the ongoing period.

Note: The maximum overall intensity should be considered as "Missing" only if all daily intensities over the period considered are "Missing."

##### 4.4.1.1.3 **Presence**

Presence of solicited reactions will be computed based on daily records during the solicited period. For any specific period, a subject would be considered to have a reaction if the intensity is greater than or equal to Grade 1 for at least one day during that period. If no data is recorded and the presence recorded by the Investigator is different from "No", the presence will be considered as "Missing."

##### 4.4.1.1.4 **Time of Onset**

Time of onset is derived from the daily intensities. It corresponds to the first day with intensity of Grade 1, Grade 2, or Grade 3.

Note: If a reaction is not continuous (i.e., reaction occurs over two separate periods of time intervened by at least one daily intensity "Missing" or "None") then the time of onset is the first day of the first occurrence.

Time of onset will be displayed by period as follows:

**Table 4.4: Categories for Time of Onset**

Period of Time of Onset	
Injection Site Reactions (D0-D7)	Systemic Reactions (D0-D14)

Period of Time of Onset	
D0 - D3	D0 - D3
D4 - D7	D4 - D7
	D8 - D14

#### 4.4.1.1.5 Number of Days of Occurrence

The “number of days of occurrence” of a solicited reaction during the solicited period is computed as the number of days the solicited reaction is present, (intensity different from none or missing between D0 and the end of the solicited period), over the daily record period. For instance, for calculating number of days of fever occurrence, only daily temperature  $\geq 38^{\circ}\text{C}$  will be considered.

Number of days of occurrence during and after the solicited period will be displayed by category (range) as follows:

**Table 4.5: Categories for Number of Days of Occurrence**

	Period of Number of Days of Occurrence	
	Injection Site Reactions	Systemic Reactions
During solicited period	1-3 days 4-7 days 8 days	1-3 days 4-7 days 8-14 days 15 days

#### 4.4.1.1.6 Overall Number of Days of Occurrence

If a reaction is ongoing at the end of the solicited period, then the overall number of days of occurrence is derived from the daily intensities and the stop date of the reaction after the end of the solicited period. The overall number of days of occurrence is:

- $(\text{stop date} - \text{last vaccination date}) + (\text{number of days of occurrence within the solicited period}) - \text{length of the solicited period} + 1$

If the stop date is missing or incomplete (contains missing data [MD]), the overall number of days of occurrence will be considered as "Missing".

**Table 4.6: Categories for Overall Number of Days of Occurrence**

	Period of Overall Number of Days of Occurrence	
	Injection Site Reactions	Systemic Reactions
Ongoing period after D7 for injection site/D14 for systemic reactions	1-3 days 4-7 days ≥ 8 days Missing	1-3 days 4-7 days 8-14 days ≥ 15 days Missing

#### **4.4.1.1.7 Ongoing**

Ongoing is derived from the last daily intensity of the solicited period and the maximum intensity of the ongoing period.

If the last daily intensity of the solicited period is Grade 1, Grade 2, or Grade 3 and maximum intensity of the ongoing period is also Grade 1, Grade 2, or Grade 3, then the reaction is considered ongoing. In any other case, the reaction will not be considered as ongoing.

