9.2.2.3.1 Immediate Post-vaccination Surveillance Period

Subjects will be kept under observation for 30 minutes after each vaccination to ensure their safety. The post-vaccination surveillance should be documented in the source document. Any AE that occurs during this period will be noted on the source document and recorded in the CRF, as follows:

- Any unsolicited systemic AE occurring during the first 30 minutes post-vaccination will be recorded on the CRF as immediate unsolicited systemic AE
- Solicited and unsolicited injection site reactions and solicited systemic reactions will be recorded and analyzed as starting on the day of vaccination
- Any SAE occurred during the first 30 minutes post-vaccination will be reported in the same way as any other SAE and to the Sponsor, according to the procedures described in [Section 10](#)

9.2.2.3.2 Reactogenicity (Solicited Reactions From Day 0 to Day 7 (Injection Site Reactions) or Day 14 (Systemic Reactions) After Each Vaccination

After each vaccination, subjects or legally acceptable representatives will be provided with a safety DC, a digital thermometer, and a flexible ruler, and will be instructed how to use them. The following items will be recorded by the subjects in the DC on the day of vaccination and for the next 7 days (ie, D0 to D7) for the solicited injection site reactions and for the next 14 days (ie, D0 to D14) for the solicited systemic reactions, until resolution:

- Daily temperature, with the route by which it was taken

- Daily measurement or intensity grade of all other solicited injection site and systemic reactions
- Action taken for each event, if any (e.g., medication)

The action taken by the subjects or legally acceptable representatives to treat any **solicited reactions** will be classified in the CRF using the following scale:

0: None
1: Medication (self-medication with an existing prescription or over-the-counter medication)
2: Health care provider contact (no new medication prescribed)
3: Health care provider contact and prescription of a new medication (health care provider instructed subject to take a new medication, either an over-the-counter medication or one requiring a written prescription)
4: Hospitalization (inpatient)

[Table 9.1](#) to [Table 9.3](#) present the injection site reactions and systemic reactions that are prelisted in the DCs and CRF, together with the intensity scales.

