#### 5.3.1.4 Intensity

For solicited reactions, missing intensities will be handled as described in Section 4.4.1.1.1.

For unsolicited non-serious AEs, missing intensities will remain missing and will not be imputed.

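### A solicited reaction with a recorded stop date after D7/D14 is coded 'not ongoing' if either grade the rule needs is Missing, so persistence beyond the solicited period can be understated

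*SAP*

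**What the plan says.** SAP 4.4.1 sets the windows: "The solicited period for solicited injection site reactions is from Day (D) 0 to D7 and from D0 to D14 for solicited systemic reactions". Counting both end days, that is 8 daily records for injection site reactions and 15 for systemic reactions.

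SAP 4.4.1.1.1 defines the grades: "Intensity will be categorized as follows: None, Grade 1, Grade 2, Grade 3, or Missing". SAP 5.3.1.4 adds no fallback for a blank grade and only refers back: "For solicited reactions, missing intensities will be handled as described in Section 4.4.1.1.1".

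SAP 4.4.1.1.7 states which variables decide persistence: "Ongoing is derived from the last daily intensity of the solicited period and the maximum intensity of the ongoing period". Both must be Grade 1, 2 or 3, and then: "In any other case, the reaction will not be considered as ongoing".

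SAP 4.4.1.1.6 brings in the stop date only after that decision: "If a reaction is ongoing at the end of the solicited period, then the overall number of days of occurrence is derived from" the daily grades together with the stop date. Table 4.6, which displays the result, covers only reactions continuing after D7 or D14.

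The protocol's reactogenicity section (9.2.2.3.2) has families record reactions beyond the window; for systemic reactions the wording is "for the next 14 days (ie, D0 to D14) for the solicited systemic reactions, until resolution". A footnote to Protocol 9.2.2.3.3 says that stop dates of related events are actively sought, and Protocol 9.2.2.3.6 treats every solicited reaction as related by convention.

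**The concern.** A missing grade is not evidence that a reaction has resolved, but the rule treats it so. It does this even when a better piece of evidence, a stop date after the window, is in the database.

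The rule is also out of step with the rest of the SAP:

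- A missing or incomplete stop date makes overall days Missing, and Table 4.6 has a Missing row for it.
- Presence with no data is Missing unless the investigator recorded a No (4.4.1.1.3).
- Missing causality is counted as related (5.3.1.2).

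So a known grade with an unknown stop date shows as Missing, while a known late stop date with an unknown grade shows as 'not ongoing'.

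At stake is the description of how many reactions outlast the solicited period and for how long. Protocol 9.2.2.2 lists duration and number of days among the items that may describe safety events. A reaction that began inside the window cannot be picked up as an unsolicited event instead, because Protocol 9.2.2.1 defines solicited reactions by symptom and onset.

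**Working it through.** The plan gives no figure for this point, so the check applies its own rules to example records. The examples are illustrative; they are not trial data.

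**Inputs**

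- Window length L: 8 (injection site) or 15 (systemic), from SAP 4.4.1.
- In-window days K: days in the solicited period with a grade other than None or Missing, from SAP 4.4.1.1.5.
- S: stop date minus last vaccination date, in days.
- Formula in SAP 4.4.1.1.6, for ongoing reactions only: overall days = S + K − L + 1.
- Ongoing status, from SAP 4.4.1.1.7: yes only if both grades are 1 to 3.

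**Check on a complete record.** An injection site reaction on every day from D0 to D20, with no grade missing: 20 + 8 − 8 + 1 = 21 days, which matches a direct count. The formula works when it is reached.

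**Records with one grade missing**

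| Case | Graded days in window | Post-window grade | Stop | Status under 4.4.1.1.7 | K | Formula, if it were applied | Table 4.6 category not filled |
|---|---|---|---|---|---|---|---|
| A, injection site | D5–D7 | Missing | D12 | not ongoing | 3 | 12 + 3 − 8 + 1 = 8 | ≥ 8 days |
| B, systemic | D10–D14 | Missing | D25 | not ongoing | 5 | 25 + 5 − 15 + 1 = 16 | ≥ 15 days |
| C, injection site | D0–D6, D7 Missing | Grade 2 | D12 | not ongoing | 7 | 12 + 7 − 8 + 1 = 12 | ≥ 8 days |
| D, injection site | D0–D7 | Missing | D20 | not ongoing | 8 | 20 + 8 − 8 + 1 = 21 | ≥ 8 days |

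In all four cases a stop date after the window is on record, and in all four the reaction is left out of the overall-days derivation. In A to C the only count left is K (3, 5 or 7 days), which falls in a lower category than the overall figure. In D, K already equals the full window, so the in-window count is in its top category and only the persistence is lost.

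**Direction.** Missing can only move a reaction from ongoing to 'not ongoing', never the reverse. Any error therefore lowers the number of reactions shown as persisting and the post-window days credited to them.

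**The case against.** Several points on the other side are sound.

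**Long reactions reported as short.** A reader might infer this, but the SAP does not say it. It gives no overall duration to a reaction that is not ongoing. The counts of 3, 5 and 7 above are in-window counts, and they are correct for Table 4.5, which is labelled for the solicited period. What can be shown is omission from Table 4.6.

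**Reactions taken to end on D7 or D14.** This is not exact either. With a blank last cell, the in-window count simply has no entry for that day and rests on the grades recorded before it.

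**Late Grade 3 peaks lost from every table.** A reader might infer this from SAP 4.4.1.1.2: "The maximum intensity during the solicited period will be computed without considering the ongoing period". That sentence limits a maximum labelled for the solicited period to that period, which is proper. SAP 4.4.1.1.7 uses a separate maximum for the ongoing period, and no table shells are available to show where that is or is not displayed. The inference is not supported.

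**Missing grades are chased.** Protocol 11.1 has the investigator clarify incomplete diary entries and explain missing information. Protocol 11.2 applies consistency checks and queries, and Protocol 13.2 has the coordinator obtain verbal clarification. These steps should keep such records few. Nor do the documents show whether the CRF accepts a stop date without a post-window grade. This limits the size of the problem but leaves the rule as written.

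**The two-grade rule has a purpose.** The 4.4.1.1.6 formula counts every day from the end of the window to the stop date, so it needs a reaction that was present at the window's end. That stands, and it constrains the fix.

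**Conclusion.** The point holds as a coding fault in a descriptive safety output. When the last in-window grade or the post-window maximum is Missing, SAP 4.4.1.1.7 returns 'not ongoing' whatever the stop date says, and the reaction leaves the overall-days derivation and Table 4.6. The count and duration of reactions persisting past the window can only be understated through this route.

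The size cannot be stated. The documents give no rate of missing grades. If no record has a late stop date together with a missing grade, the stop-date part of the fix changes nothing.

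The conclusion assumes that the rule is programmed as written and that such a record can exist in the CRF. Presence, time of onset, in-window maximum intensity and all primary and secondary non-inferiority tests are unaffected, and safety is descriptive throughout (SAP 5.1.2.2). This is a minor correction that is worth making.

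**What to change.** Reword SAP 4.4.1.1.7 for a reaction present in the solicited period:

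1. If the last daily grade is Grade 1 to 3 or Missing, class the reaction as ongoing when either a stop date after the window or a post-window Grade 1 to 3 is recorded.
2. If neither is recorded and a required grade is Missing, set ongoing status and overall days to Missing, not to No.
3. If the last daily grade is None, keep the reaction as 'not ongoing'.

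Step 3 is needed. A wider rule, under which any later stop date or grade would suffice, would count symptom-free days. Take injection site pain on D0–D1, None on D2–D7 and a recurrence on D20–D21. The formula would give 21 + 2 − 8 + 1 = 16 days, against 4 days with symptoms. The same can happen under step 1 if a blank last day follows days graded None, so such records should be queried first.

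SAP 4.4.1.1.6 should also state what overall duration, if any, a 'not ongoing' reaction receives.

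The cost is a few sentences and minor reprogramming, with no new data collection. A few reactions may move to longer or Missing categories.

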#### **4.4.1.2 Unsolicited Non-serious AEs**

##### **4.4.1.2.1 Intensity**

Intensity will be categorized as follows: None, Grade 1, Grade 2, Grade 3, or Missing. For unsolicited non-serious adverse events (AEs) the intensity will be recorded by the Investigator for AEs whose scale is not a measure. For measurable AEs that have the same preferred term (PT) as a solicited reaction, the intensity will be calculated at the time of the statistical analysis.

##### **4.4.1.2.2 Last Vaccination**

Last vaccination before an unsolicited non-serious AE is derived from the visit numbers provided in the clinical database and is calculated as follows:

- If an unsolicited non-serious AE has a non-missing visit number, the visit number should be used to determine the last vaccination before the unsolicited non-serious AE
- If the visit number is missing, then the start date should be used to determine the last vaccination before the unsolicited non-serious AE

##### **4.4.1.2.3 Time of Onset**

Time of onset in days following the vaccination will be computed as follows:

- Time of onset = start date – date of previous vaccination

If the start date of the AE is the same as the last vaccination date, then the onset is “0”.

If one of the dates is partially missing, time of onset will be considered as “Missing”. Events that occur before vaccination (negative time of onset) will not be included in the analyses but will be listed separately. The unsolicited non-serious AEs will be analyzed within 28 days after vaccination, which corresponds to AEs with a time of onset between 0 and 28 days after vaccination or missing. An AE with missing time of onset will be considered to have occurred just after the vaccination indicated by the visit number, so will be included in these tables.

Time of onset will be displayed by period as follows:

- D0-D3
- D4-D7
- D8-D14
- $\geq$  D15
- Missing

#### 4.4.1.2.4 Duration

The duration will be computed as: Duration = stop date of event - start date of event + 1.

If start or stop dates are unfilled (“blank”) or missing (contain “MD”) or ongoing is ticked, then the duration will be considered as “Missing.”

If the start date of the AE is the same as the last vaccination date, then the duration is 1 day.

Duration will be displayed by period as following:

- 1-3 days
- 4-7 days
- 8-14 days
- 15 days or more
- Missing

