9.2.2.2 Safety Endpoints

Cervarix and CYD dengue vaccine safety in each group:

- Occurrence of immediate AEs reported within 30 minutes after each and any injection
- Occurrence of solicited (ie, pre-listed in the subject's DC and CRF) injection site reactions (pain, erythema, and swelling) occurring up to 7 days after each and any injection
- Occurrence of solicited systemic reactions (fever, headache, malaise, myalgia, and asthenia) occurring up to 14 days after each and any injection
- Occurrence of unsolicited AEs occurring up to 28 days after each and any injection
- Occurrence of non-serious AESIs* reported within 7 days following each and any injection
- Occurrence of SAEs, including serious AESIs (with specific time windows according to the type of AESI*) throughout the trial
- Occurrence of hospitalized VCD cases throughout the trial (ie, from D0 through end of the study)

*Hypersensitivity/allergic reactions (serious or not) within 7 days after each CYD dengue vaccine injection, serious viscerotropic disease within 30 days after each CYD dengue vaccine injection, serious neurotropic disease within 30 days after each CYD dengue vaccine injection; serious dengue cases requiring hospitalization will be reported during the entire study.

Depending on the item, these could include: nature (Medical Dictionary for Regulatory Activities [MedDRA] preferred term), time of onset, duration, number of days of occurrence, Grade of

^a All injection site AEs are considered to be related to vaccination and are therefore all *injection site reactions*.

severity, relationship to vaccine, action taken, whether the event/reaction led to early termination from the study, seriousness, or outcome.

Hospitalized suspected dengue case is defined as an acute febrile illness with diagnosis of dengue requiring hospitalization (with bed attribution). In such cases, 1 unplanned acute blood sample (within the first 5 days after fever onset) will be collected for virological confirmation of hospitalized suspected dengue case. A suspected case will be considered VCD if there is a detection of WT dengue virus by dengue NS1 Ag ELISA and/or dengue RT-PCRs (at the GCI or GCI designated laboratory).

Note: Acute blood sample for all hospitalized suspected dengue cases should be collected within the pre-specified timeframe as described above. If this cannot be accomplished, this sample should still be obtained as soon as possible thereafter, for IDMC severity assessment.

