#### **4.4.1.3.3 Duration**

Duration will be computed using the same methodology as for unsolicited non-serious AEs described in Section 4.4.1.2.4 .

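### The SAP's 1-day rule for unsolicited AEs and SAEs that start on the vaccination day contradicts its own duration formula and shortens any such event that runs past that day

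*SAP*

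**What the plan says.** SAP 4.4.1.2.4 gives three rules for the duration of unsolicited non-serious AEs.

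- The general formula: "Duration = stop date of event - start date of event + 1".
- A rule for incomplete records. If a start or stop date is blank or missing, "or ongoing is ticked, then the duration will be considered as" missing.
- A rule for vaccination-day onset: "If the start date of the AE is the same as the last vaccination date, then the duration is 1 day".

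Duration is then displayed in five categories: 1-3 days, 4-7 days, 8-14 days, "15 days or more", and missing.

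SAP 4.4.1.3.3 extends all of this to SAEs: "Duration will be computed using the same methodology as for unsolicited non-serious AEs".

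Protocol 9.2.2.2 names duration among the descriptors that may be reported for the safety endpoints: "time of onset, duration, number of days of occurrence".

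The section just before, SAP 4.4.1.2.3, uses the same condition for a different quantity: "If the start date of the AE is the same as the last vaccination date, then the onset is" zero.

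**The concern.** The vaccination date determines time of onset but has no bearing on how long an event lasts. In 4.4.1.2.3 the condition is correct, because an event starting on the day of injection has onset zero. In 4.4.1.2.4 the same condition is attached to duration, where it is wrong unless the event also ends that day. The likely explanation is a drafting slip: the intended condition was probably that the start date equals the stop date.

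The SAP is the specification from which the tables are programmed, and here it gives two incompatible instructions for one variable. The error runs one way: where the stop date is known, the sentence can only shorten a duration. The exposed events are of some interest.

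- Unsolicited systemic AEs within 30 minutes of injection (Protocol 9.2.2.3.1) start on Day 0, barring an injection close to midnight.
- Unsolicited injection site reactions with Day 0 onset are exposed. Induration, for example, is named as a potential effect in Protocol 1.3.2 but is not on the solicited list.
- Hypersensitivity events of special interest and other SAEs with Day 0 onset are exposed.

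The schedule also differs by arm. A fully vaccinated Group 1 subject has three vaccination days (D0, M6, M12) and a Group 2 subject has five (D0, M1, M6, M7, M13). A rule keyed to the vaccination day could therefore affect the two groups' duration tables unequally.

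**Working it through.** **Inputs.** The formula, the vaccination-day rule, the missing rule and the display categories all come from SAP 4.4.1.2.4. The solicited-reaction derivations come from SAP 4.4.1.1.5 and 4.4.1.1.6. Day 0 is the vaccination day.

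**Step 1: when is the stated 1 day right?** With start = 0, the formula gives stop − 0 + 1. This equals 1 only if stop = 0. The stated figure is therefore reproduced for events that begin and end on Day 0, and for no others.

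**Step 2: Day 0 onset with a known stop date.**

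| Stop day | Formula (stop − 0 + 1) | Correct category | Literal rule | Category under the rule |
|---|---|---|---|---|
| 0 | 1 | 1-3 | 1 | 1-3 |
| 1 | 2 | 1-3 | 1 | 1-3 |
| 2 | 3 | 1-3 | 1 | 1-3 |
| 3 | 4 | 4-7 | 1 | 1-3 |
| 7 | 8 | 8-14 | 1 | 1-3 |
| 9 | 10 | 8-14 | 1 | 1-3 |
| 14 | 15 | 15 or more | 1 | 1-3 |
| 27 | 28 | 15 or more | 1 | 1-3 |

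Stops on Day 1 or 2 give a wrong value in the right category. A stop on Day 3 or later gives a wrong value in the wrong category.

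**Step 3: the same event starting one day later.** An 8-day event from Day 1 to Day 8 gives 8 − 1 + 1 = 8 days, category 8-14. An 8-day event from Day 0 to Day 7 is set to 1 day. Under the literal rule, the reported duration depends on the onset day as well as on the length of the event.

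**Step 4: Day 0 onset, ongoing or no stop date.** The missing rule gives missing; the vaccination-day rule gives 1 day. Both conditions are met and 4.4.1.2.4 does not rank them. SAP 5.3.1.5 says that missing stop dates are not imputed. That sits better with missing, but it does not settle how duration is derived.

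**Step 5: solicited reactions.** In 4.4.1.1.5 the number of days of occurrence "is computed as the number of days the solicited reaction is present", with no vaccination-day exception. In 4.4.1.1.6 a reaction that outlasts the solicited period is counted as (stop − vaccination date) + days within the period − length of the period + 1. Taking period lengths of 8 and 15 days (an assumption that counts D0), for continuous reactions from Day 0:

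- injection site reaction stopping on Day 9: 9 + 8 − 8 + 1 = 10 days, correct;
- systemic reaction stopping on Day 20: 20 + 15 − 15 + 1 = 21 days, correct.

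**The case against.** The strongest answer is that little depends on this sentence. All safety analyses are descriptive (SAP 5.1.2.2). Protocol 9.2.2.2 lists duration only as something that may be shown, depending on the item. SAP Table 5.1 calls for numbers and percentages of subjects and numbers of events for unsolicited AEs, and none of these depends on duration. Start and stop dates are collected (Protocol 9.2.2.3.3), so true durations can be recovered. The general formula comes first and is correct, and a programmer may have followed it; the documents do not show what was programmed. All of this stands, and it is why the severity is low. It does not remove the contradiction, because nothing elsewhere in the protocol or SAP corrects or limits the sentence.

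A reader might go further and infer that every AE starting on the vaccination day, and so the events most likely to be caused by the vaccines, will be reported as short. The documents do not support that. Solicited reactions have their own derivation, which is sound. Protocol 9.2.2.3.6 counts all solicited systemic reactions and all injection site AEs as related by convention, and the solicited ones among these are unaffected. Related unsolicited events starting on Day 1 or later are also unaffected.

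Nor can it be said that every Day 0 event longer than 1 day lands in the wrong category, since 2- and 3-day events do not. For ongoing events the outcome is undetermined; it is not certain that they would be shown as 1 day.

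**Conclusion.** The rule is wrong as written, within a narrow scope. It applies to unsolicited non-serious AEs and, by cross-reference, to SAEs that start on the last vaccination date. Applied literally, each such event with a known stop date after Day 0 gets too short a duration, and each one lasting 4 days or more is displayed as 1-3 days. For such events that are ongoing or have no stop date, the SAP gives two answers and does not choose between them.

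The number of events affected cannot be estimated, because the documents give no expected frequency of Day 0 unsolicited AEs or SAEs, or of how long they last. The possible imbalance between arms is likewise unquantified. The conclusion assumes that the sentence is applied as it reads.

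Only the descriptive duration outputs are exposed. Event counts, time of onset, intensity, causality and the non-inferiority tests do not change. This is a low-severity correction.

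**What to change.** In SAP 4.4.1.2.4, either delete the sentence or replace its reference to the last vaccination date with the stop date. The second option is redundant with the formula but harmless. Add a short statement that the missing rule takes precedence whenever a date is missing or the event is ongoing. SAP 4.4.1.3.3 inherits the correction by cross-reference and needs no edit of its own.

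Then check how duration was derived in the programs. If the literal rule was coded, rerun the duration outputs for unsolicited AEs and SAEs. The cost is one or two sentences in the SAP and a check of one derived variable. No new data are needed and no other result changes.
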